#### 2.2 Study Design Overview

A total of 150 subjects will be enrolled into five treatment arms with 30 subjects for each arm. The treatment period will last for 14 days and the post-treatment period will follow till Month 6. Post-study ivermectin that kills microfilaria will be given to all participants after nodulectomy at Month 6.

The schematic of the study is shown in Figure 1.

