#### 2.3 Treatment Assignment and Blinding

Subjects will be randomized continuously 1:1:1:1:1 into one of five parallel treatment arms through an Interactive Response Technology (IRT) system. Randomization will be

stratified by the number of operable sites with onchocercomata (one site vs. more than one site).

The five treatment arms are defined as follows:

- Arm A: 7 days of ABBV-4083 400 mg + albendazole matching placebo followed by 7 days of ABBV-4083 matching placebo
- Arm B: 7 days of ABBV-4083 400 mg + albendazole matching placebo followed by 7 days of ABBV-4083 400 mg
- Arm C: 7 days of ABBV-4083 400 mg + albendazole 400 mg followed by 7 days of ABBV-4083 matching placebo
- Arm D: 3 days of ABBV-4083 400 mg + albendazole 400 mg followed by 4 days of ABBV-4083 400 mg + albendazole matching placebo followed by 7 days of ABBV-4083 matching placebo
- Arm E: 7 days of ABBV-4083 matching placebo + albendazole 400 mg followed by 7 days of ABBV-4083 matching placebo

The treatment assignment will remain blinded to the Investigator, as well as clinical, pharmacy, and laboratory personnel, and the Sponsor, including statistics and data management personnel and the study monitor, until the final database lock, after all Part 1 subjects are followed to Month 6 or have prematurely discontinued from follow-up.

Toxicity of the treatments will be monitored throughout the study. If > 10% of the subjects in any arm meet any of the protocol-specified toxicity criteria after 15 subjects are enrolled in each arm, the Data and Safety Monitoring Board (DSMB) may recommend halting enrolment into arms of the same or longer duration with or without albendazole and continuing enrolment in those arms of the shorter duration. The enrolment of the closed arms may be reopened using a lower dose of ABBV-4083 at 300 mg QD with the same duration and same combination (with or without albendazole) as the original arm, in which case enrolment will continue until 30 subjects have been enrolled at that dose. However, subjects who have already received 400 mg QD ABBV-4083 in the halted arm

and have not experienced dose-limiting toxicity will be kept on the same dose until treatment completion.

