#### 7.1 Demographics and Baseline Characteristics

Continuous demographic variables include age, weight, height, and body mass index (BMI). Categorical demographic variables include sex, race, age (< 40, or  $\ge$  40 years), weight (< 60 or  $\ge$  60 kg), and BMI (< 18, 18 to < 25, or  $\ge$  25 kg/m^2).

Baseline characteristics include symptoms of onchocerciasis disease (ocular or skin), number of operable sites with onchocercomata (continuous and categorical: 0, 1 or > 1), number of palpated nodules (continuous and categorical: 0, 1 or > 1), skin microfilarial density (continuous and categorical:  $\leq 5$  or > 5 mf/mg), district of residence (Kimpese, Masa, Masi-Manimba, Moanza, Nsonampangu, Pay Kongila, or Other), number of years resident in endemic area (continuous), number of previous ivermectin rounds (continuous and categorical 0, 1, or > 1), time since the last ivermectin administration (continuous and categorical,  $\leq 1$  year or > 1 year), parasitological co-infections (e.g., *Loa loa* or *Schistosoma haematobium*). Baseline continuous laboratory values include aspartate aminotransferase (AST), alanine aminotransferase (ALT), alkaline phosphatase (AP), creatinine clearance, estimated glomerular filtration rate (eGFR), total bilirubin, and albumin.

"Baseline" refers to the last non-missing observation before the first administration of study drug.

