#### 10.3 Analysis of Laboratory Data

Haematology variables to be summarized include: haematocrit, haemoglobin, red blood cells (RBC), white blood cells (WBC), neutrophils, lymphocytes, monocytes, eosinophils, basophils, platelets.

Chemistry variables to be summarized include: aspartate aminotransferase (AST), alanine aminotransferase (ALT), alkaline phosphatase (AP), glucose, creatinine, eGFR, blood urea nitrogen (BUN), total bilirubin, albumin, total protein, chloride, sodium, potassium and calcium.

Each laboratory variable will be summarized for all time points (Baseline, Day 3, Day 6, Day 13, Month 3, and end of study follow-up) with the number of non-missing observations, mean and standard deviation, median, Q1, Q3, minimum and maximum. Mean change from baseline to each applicable post-baseline visit will be summarized for all laboratory variables, with the number of observations, baseline mean, and visit mean. The change from baseline mean, standard error, and 95% confidence interval will be presented for the mean change from baseline within each treatment arm and difference between the active arms and the control arm (A, B, C, D vs. E) and between all active arms and the control arm (A – D vs. E) using separate ANOVA models.

Changes in chemistry and hematology laboratory parameters will be tabulated using shift tables, for laboratory parameters that have a normal range reported. Laboratory data values will be categorized as low, normal, or high based on the normal ranges of the laboratory used for each sample. Shift tables from baseline to the minimum and maximum values during the Treatment Period will be created. In these shift tables, the number and percentage of subjects with baseline values within or above the normal range (baseline high or normal) and a minimum value below the normal range (post-baseline low during treatment) and the number and percentage of subjects with baseline values within or

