#### 10.4 Analysis of Vital Signs

Vital sign measurements of systolic and diastolic blood pressure, heart rate, resting respiratory rate and temperature will be summarized.

Each vital sign variable will be summarized for all time points (Baseline, Day 3, Day 6, Day 13, Month 3, and end of study follow-up) with the number of non-missing observations, mean and standard deviation, median, Q1, Q3, minimum, and maximum. Mean change from baseline to each applicable post-baseline visit will be summarized for each vital sign variable, with the number of observations, baseline mean, and visit mean. The change from baseline mean, standard error, and 95% confidence interval will be presented for the mean change from baseline within each treatment group and difference between treatment arms (A, B, C, D vs. E) and between all active arms and the control arm (A – D vs. E) using separate ANOVA models.

Vital signs variables will be evaluated based on potentially clinically important (PCI) criteria (Appendix C) using all post-baseline values. For each vital sign PCI criterion, the number and percentage of subjects who have a vital sign value meeting the criteria will be summarized. Listings will be provided to summarize subject-level vital sign data for subjects meeting PCI criteria.

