		• Section 9.5 For ophthalmological exam outcomes, added blurred vision and night blindness to summary of clinical grade and clarified that anterior uveitis would have separate grades for number of cell/field and flare). For summaries of change from baseline in ocular and skin exam, summary category of "similarity" was changed to "no change."
		• Section 10.2.2, Section 10.2.3, and Section 10.2.4 Clarified that summaries of treatment-emergent AEs based on relationship to study drug and of treatment- emergent AEs leading to discontinuation of study drug would be performed with study drug defined in 4 ways: ABBV-4083, albendazole, ABBV-4083 and/or albendazole, and ABBV-4083 and albendazole. The description of the summary of all deaths was clarified to include time periods.
		• Section 10.2.4 Added listings of all SAEs and all deaths.
		• Section 10.3 Deleted statement about including laboratory testing due to an SAE because SAE-related laboratory assessments are not collected in a format that can be summarized. Removed summary of creatinine clearance and added eGFR because eGFR is collected in the study and is more applicable to the study population. Removed summary of urinalysis data because only abnormal results are collected. Clarified that changes from baseline would be analyzed using ANOVA models. Provided more detail about the analyses related to normal range shift for laboratory parameters. Added separate summaries for a maximum of Grade 3 and a maximum of Grade 4 for graded laboratory parameters. Added an eDISH plot for AST versus bilirubin.
		• Section 10.4 Clarified that changes from baseline would be analyzed using ANOVA models. Clarified that
		evaluation of potentially clinically important criteria are to be assessed using all post-baseline values.

Version	Date	Summary
		• Section 10.5 Deleted Month 3 visit summary because ECG data are not collected at Month 3. Clarified that only investigator interpretation of ECG would be summarized and that percentages would be calculated using only interpretable tests.
		
 
Appendix A Added the protocol deviation categories.
 
Appendix B Clarified that any subject taking a prohibited medication will be documented as a protocol deviation.
 

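### Between-arm differences in laboratory and vital-sign change come from ANOVA without baseline as a covariate; adding it would usually tighten these descriptive safety intervals at almost no cost

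*SAP*

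**What the plan says.** For each laboratory variable, SAP 10.3 states: "The change from baseline mean, standard error, and 95% confidence interval will be presented for the mean change from baseline within each treatment arm". The same sentence adds the differences of A, B, C and D from E, and of A to D together from E, and closes with "using separate ANOVA models". SAP 10.4 sets up the same output for vital signs: "difference between treatment arms (A, B, C, D vs. E) and between all active arms and the control arm", again by separate ANOVA models. Neither section names a covariate.

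The wording is deliberate. The SAP version history records for both sections: "Clarified that changes from baseline would be analyzed using ANOVA models". SAP 7.1 defines baseline for the whole plan; it "refers to the last non-missing observation before the first administration of study drug". On size, SAP 2.2 states: "A total of 150 subjects will be enrolled into five treatment arms with 30 subjects for each arm". Randomisation is stratified only by number of operable sites (SAP 2.3).

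The Protocol synopsis calls the safety analysis descriptive. Protocol 10.8 asks for a summary of mean change from baseline and names no model. Neither document adds a baseline-adjusted laboratory or vital-sign comparison elsewhere.

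**The concern.** Subtracting baseline removes its influence fully only if the later value moves one for one with it. Laboratory values and vital signs fluctuate, so a high first reading tends to be followed by a lower one. If one arm starts higher than Arm E by chance, its mean change will tend to look lower for that reason alone, and part of the imbalance stays in the comparison with the opposite sign. The ordinary fluctuation that a baseline covariate would absorb also stays in the error term and widens the interval.

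Imbalances will occur. SAP 10.3 lists 24 laboratory variables and SAP 10.4 five vital signs, so there are 29 x 4 = 116 comparisons of a single arm with E, each with its own baseline difference. About 13% of such differences exceed 1.5 standard errors by chance, which is roughly 15 of 116. Since the same baseline is subtracted at every visit, one imbalance recurs down the whole column of visits and can pass for a consistent drug effect, or hide one.

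Liver tests are the potential safety effect that the Protocol singles out (2.3.2 and 3.5.1.1). The other laboratory and vital-sign outputs in SAP 10.3 and 10.4 are counts, listings and plots, so these are the only between-arm intervals a reader will have on those measures.

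**Working it through.** **Inputs.** From the documents: five arms of 30 (SAP 2.2), equal allocation (SAP 2.3), change from baseline as outcome and the contrasts above (SAP 10.3 and 10.4). Assumed: rho from 0.3 to 0.9; a ratio k of baseline SD to visit SD of 1, then 0.7; the same baseline slope in every arm. The documents give no SD, correlation, interval width or power for these measures, so there is no planned figure to reproduce.

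**Formulas.** With baseline SD s0 and visit SD s1, the variance per subject is:

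- change score: s0² + s1² - 2·rho·s0·s1
- with baseline as covariate: s1²(1 - rho²)

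The first exceeds the second by (s0 - rho·s1)², so apart from one degree of freedom the covariate cannot widen the interval. The variance ratio is (1 - rho²)/(1 + k² - 2·rho·k), which becomes (1 + rho)/2 when k = 1. Interval width goes with its square root.

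**Equal SDs (k = 1).** Half-widths are for one active arm against E with 30 per arm, in SD units, from a single five-arm model. For ANOVA the half-width is t(145 df) x √(2(1-rho)) x √(2/30). For ANCOVA it is t(144 df) x √(1-rho²) x √(2/30) x √(1 + 1/143).

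| rho | variance ratio | narrowing, large sample | half-width, ANOVA | half-width, ANCOVA | narrowing, 30 per arm |
|---|---|---|---|---|---|
| 0.3 | 0.65 | 19.4% | 0.604 | 0.489 | 19.1% |
| 0.5 | 0.75 | 13.4% | 0.510 | 0.444 | 13.1% |
| 0.7 | 0.85 | 7.8% | 0.395 | 0.366 | 7.5% |
| 0.9 | 0.95 | 2.5% | 0.228 | 0.223 | 2.2% |

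For A to D pooled against E, the half-width falls from 0.403 to 0.351 at rho 0.5 and from 0.313 to 0.289 at rho 0.7. To match ANCOVA with 30 per arm, ANOVA would need 2 x 30/(1 + rho) per arm: 40 at rho 0.5 and about 35 at rho 0.7. The SAP does not say what makes the models separate; the large-sample ratio does not depend on it.

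**Unequal SDs (k = 0.7).**

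- rho 0.3: 0.91/1.07 = 0.850, square root 0.922, 8% narrower
- rho 0.5: 0.75/0.79 = 0.949, square root 0.974, 3% narrower
- rho 0.7: 0.51/0.51 = 1, no gain
- rho 0.9: 0.19/0.23 = 0.826, square root 0.909, 9% narrower

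The gain vanishes where rho equals k and returns on either side.

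**Residual shift.** With equal SDs, the change-score difference moves by -(1 - rho) times the baseline difference. One standard error of the baseline difference is √(2/30) = 0.258 SD. The shift is then -0.5 x 0.258 = -0.129 SD at rho 0.5 and -0.3 x 0.258 = -0.077 SD at rho 0.7.

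**Simulation (equal SDs, five arms of 30, 4,000 runs per rho).** Width ratios of ANOVA to ANCOVA were 1.236, 1.150, 1.082 and 1.022 at rho 0.3, 0.5, 0.7 and 0.9, in line with the table. Overall coverage was nominal for both: 94.2% to 95.4% for ANOVA and 94.4% to 95.0% for ANCOVA. In runs where the baseline difference exceeded 1.5 standard errors, ANOVA coverage was about 80%, 87%, 90% and 92% at the four values of rho; ANCOVA stayed between 94% and 96%.

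**The case against.** The case for leaving the plan alone has four parts, and most of it stands.

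- **Baseline is already used.** A reader might infer that the plan ignores baseline. It does not. Baseline is subtracted, baseline means are displayed, shift tables start from the baseline category, and a graded value counts only if its grade is more extreme than at baseline. What is missing is baseline as a covariate in the between-arm model.
- **The inference is valid.** A reader might infer that the intervals are biased. Over all randomisations they are not, and coverage is nominal. The distortion exists only given a chance imbalance.
- **No decision rule uses these intervals.** A reader might infer that the choice of regimens for Part 2 turns on them. Protocol 10.9 bases selection on all available data, including overall safety and tolerability. The toxicity rule in Protocol 3.5.2.2 counts subjects meeting per-subject criteria. The hepatotoxicity thresholds in SAP 10.3 and the vital-sign criteria in SAP 10.4 are also per subject. There is no safety hypothesis or margin.
- **The gain is uncertain.** It depends on rho and on the SD ratio, and neither is given. For liver tests, exclusion criterion 11 (Protocol 6.2) truncates baseline values while on-treatment values are free to spread, so a baseline SD below the visit SD is plausible. At some combinations the gain is nil.

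A reader might also want the liver tests analysed on the log scale. Nothing in this argument requires that, and it would replace the mean change named in Protocol 10.8 with a ratio.

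These points limit the consequence. None of them favours ANOVA over ANCOVA.

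**Conclusion.** The point holds as a free improvement. The between-arm intervals in SAP 10.3 and 10.4 are valid on average, but in general wider than they need be and exposed to chance baseline differences in individual comparisons. With equal SDs the avoidable width ranges from about 19% at rho 0.3 to about 2% at rho 0.9. With a baseline SD 0.7 of the visit SD it is 8%, 3% and 0% at rho 0.3, 0.5 and 0.7. Both rho and the SD ratio are assumptions, so no single percentage should be quoted as the gain. The documents support neither a finding of invalid safety inference nor a claim that a safety trigger or the selection of regimens would change.

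**What to change.** In SAP 10.3 and 10.4, take the between-arm differences and their 95% intervals (each of A, B, C and D against E, and A to D pooled against E) from an ANCOVA of change from baseline on treatment arm, with the baseline value of the same parameter as covariate. Keep the unadjusted within-arm mean changes, standard errors and intervals as planned.

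The cost is one model term, one degree of freedom and a line in the version history. No new data are needed, and no subject is lost, because a change score already requires a baseline value. A footnote should say that the adjusted difference need not equal the difference between the displayed unadjusted means.

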3.5.1.2 Potential and Identified Risks of Albendazole

Treatment with albendazole has been associated with mild to moderate elevations on hepatic enzymes that usually normalize upon discontinuation of therapy. Cases of acute liver failure of uncertain causality and hepatitis have also been reported. Subjects with abnormal transaminases before starting albendazole therapy should be carefully monitored during treatment. Liver tests should be obtained before the start of therapy and on regular basis for long duration treatment courses.

Treatment with albendazole has been shown to occasionally cause myelosuppression and therefore blood counts should be performed at the start of therapy and regularly for long duration treatment courses. Subjects with liver disease appear to be more susceptible to myelosuppression and warrant closer monitoring.

Treatment with albendazole for neurocysticercosis may cause symptoms associated with an inflammatory reaction following the death of the parasite (e.g. seizures, increased intracranial pressure and focal signs). Pre-existing neurocysticercosis may be also uncovered in patients treated with albendazole for other conditions, especially in areas with high taeniasis infection.

Treatment with albendazole has been shown to be teratogenic and embryotoxic in animal studies. Therefore, women of childbearing age should initiate treatment only after a negative

pregnancy test and should be advised to use highly effective method of contraception up to 1 month after last intake of albendazole. See in addition the albendazole package inserts for further information. 57,64

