10.8 Statistical Analysis of Safety

All safety analyses will be performed on the Safety Population, which consists of all subjects who received at least one dose of IMP. Safety will be assessed by AEs, laboratory tests, vital signs, and ECG variables. Details of the analyses will be provided in the Statistical Analysis Plan.

AEs will be coded using the Medical Dictionary for Regulatory Activities (MedDRA). A TEAE is defined as an AE with an onset date that is after the first intake of IMP and no more than 30 days after the last intake of IMP. The number and percentage of subjects experiencing TEAEs will be tabulated using MedDRA system-organ class and preferred term, as well as by severity and by relationship to the IMP as assessed by the Investigator. Summaries of SAEs, deaths, AEs leading to discontinuation will also be provided.

For laboratory test and vital signs variables, mean change from baseline and percentage of subjects with on-treatment laboratory values of CTCAE 5.0 adapted scale grade 3 or 4 will be summarised.

10.9 Interim Analysis of Part 1 and DSMB Recommendation to Proceed to Part 2

Once subjects in Part 1 have completed or prematurely discontinued the study, up to and including nodulectomy at 6 months, a database lock for Part 1 database and an interim analysis of data from Part 1 will be conducted by the Sponsor and the randomisation code unblinded. The unblinded data will be reviewed by the Sponsor and the DSMB (see Section 13.3), for futility and risk/benefit ratio. Taking into account the recommendations of the DSMB, especially regarding the safety assessment of the data, the Sponsor will decide whether or not to proceed to Part 2, and with which dose regimens.

Selection of up to two acceptable/suitable doses / regimens for Part 2 will be based on analysis of all of available unblinded data from Part 1, including safety and tolerability of ABBV-4083 and ABBV-4083 + albendazole, *Wolbachia* depletion, disruption of embryogenesis and an exploratory surrogate marker, microfilaria *Wolbachia*, observed at Months 3 and 6.

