# 1.0 Introduction

This Statistical Analysis Plan (SAP) describes the statistical analyses of Part 1 only for ABBV-4083 Study B18-894/DNDi-TYL-01 "A Phase-II, Randomised, Double-blind, Parallel-group, Proof-of-concept Trial to investigate ABBV-4083 given for 7 or 14 Days or in combination with Albendazole in Subjects with *Onchocerca volvulus* Infection." Part 2 will have a separate clinical database with a separate SAP and database lock.

Part 1 of Study B18-894/DNDi-TYL-01 investigates the safety, tolerability, efficacy for duration-ranging and pharmacokinetics of ABBV-4083 with or without albendazole in subjects infected with *Onchocerca volvulus*.

The analyses of pharmacokinetic endpoints and their relationship to efficacy and safety endpoints will not be covered in this SAP.

The SAP will not be updated in case of administrative changes or amendments to the protocol unless the changes impact the analysis.

Unless noted otherwise, all analyses will be performed using SAS Version 9.4 (SAS Institute Inc., Cary, NC 27513) or later under the UNIX operating system.

All analyses in this SAP are consistent with what is described in the study protocol unless otherwise noted in Section 13.0.

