below the normal range (baseline low or normal) and a maximum value above the normal range (post-baseline high during treatment) will be summarized. Similar shift tables will be created for the shift from baseline to the final post-baseline value where the number and percentage of subjects with baseline values within or above the normal range (baseline high or normal) and the final post-baseline value below the normal range and the number and percentage of subjects with baseline values within or below the normal range (baseline low or normal) and the final post-baseline value above the normal range (baseline low or normal) and the final post-baseline value above the normal range will be summarized.

The number and percentage of subjects with a maximum of Grade 3, a maximum of Grade 4, and a maximum of at least Grade 3 (CTCAE 5.0) for the laboratory parameters during treatment as defined in Appendix C will be summarized. The post-baseline value must be in a toxicity grade that is more extreme than the toxicity grade corresponding to the baseline value, if a baseline value is available, in order to be counted. A listing of all relevant laboratory parameters will be provided for each subject who had an increase to Grade 3 or higher.

The following criteria will be used to assess potential hepatotoxicity during treatment.

- $ALT > 3 \times ULN, > 5 \times ULN, > 10 \times ULN, > 20 \times ULN$
- $AST > 3 \times ULN, > 5 \times ULN, > 10 \times ULN, > 20 \times ULN$
- bilirubin >  $1.5 \times ULN$ , >  $2 \times ULN$
- ALT and/or AST >  $3 \times$  ULN and bilirubin >  $1.5 \times$  ULN
- ALT and/or AST >  $3 \times$  ULN and bilirubin >  $2 \times$  ULN
- ALT > 3 × ULN and bilirubin >  $1.5 \times ULN$
- ALT > 3 × ULN and bilirubin > 2 × ULN
- Alkaline phosphatase (ALP)  $> 1.5 \times ULN$

The number and percentage of subjects with laboratory values meeting the above criteria during treatment will be summarized. Listing of ALT, AST, total bilirubin, and alkaline phosphatase values will be provided for each subject who met one or more of the criteria defined above.

An Evaluation of Drug Induced Serious Hepatotoxicity (eDISH) plot of the maximum post-baseline ALT value (as a multiple of the ULN) versus the maximum post-baseline bilirubin value (as a multiple of the ULN) during treatment, not necessarily concurrent, will also be utilized to assess for potential hepatotoxicity. A similar plot will be produced for AST versus bilirubin.

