#### Appendix C. Potentially Clinically Important Criteria for Safety Endpoints

#### Table C-1.Definitions of Toxicity Grades 1, 2, 3, and 4 for Laboratory Values

Test	Grade 1	Grade 2	Grade 3	Grade 4
ALT*	> ULN – 3 × ULN if baseline was normal or missing; 1.5 – 3 x baseline if baseline was abnormal	> 3 - 5 × ULN*	> 5 - 20 × ULN*	> 20 × ULN*
AST*	> ULN – 3 × ULN if baseline was normal or missing; 1.5 – 3 x baseline if baseline was abnormal	> 3 - 5 × ULN*	> 5 - 20 × ULN*	> 20 × ULN*
ALP*	> ULN – 2.5 × ULN if baseline was normal or missing; 2 – 2.5 x baseline if baseline was abnormal	> 2.5 – 5 × ULN*	> 5 - 20 × ULN*	> 20 × ULN*
Bilirubin*	> ULN – 1.5 × ULN if baseline was normal or missing; 1- 1.5 x baseline if baseline was abnormal	> 1.5 – 3 × ULN*	> 3 - 10 × ULN*	> 10 × ULN*
Haemoglobin (female)+	11.0 - 12.0 g/dL	9.5 - 10.9 g/dL	8.0-9.4  g/dL	< 8.0  g/dL
Haemoglobin (male)+	12.5 - 13.5 g/dL	10.5 - 12.4 g/dL	8.5 - 10.4 g/dL	< 8.5 g/dL
White blood cells	$<$ LLN $- 3.0 \times 10^{9}$ /L	$< 3.0 - 2.0 \times 10^{9}/L$	$< 2.0 - 1.0 \times 10^{9}/L$	$< 1.0 \times 10^{9}/L$
Platelets	$<$ LLN $-$ 75.0 $\times$ 10  /L	$< 75.0 - 50.0 \times 10^{9}/L$	$< 50.0 - 25.0 \times 10^{9}/L$	$< 25.0 \times 10^{9}/L$
Glucose (decreased)	< LLN $-$ 3.0 mmol/L	< 3.0 – 2.2 mmol/L	< 2.2 – 1.7 mmol/L	< 1.7 mmol/L
Creatinine	$>$ ULN $- 1.5 \times$ ULN	> 1.5 – 3 × ULN	$> 3 - 6 \times ULN$	$> 6 \times ULN$
eGFR	$< 90 - 60 \text{ mL/min}/1.73 \text{m}^2$	< 60 - 30 mL/min/1.73m 	< 30 - 15 mL/min/1.73m 	< 15 mL/min/1.73m 
Albumin	< LLN $- 3 g/dL$	< 3 - 2  g/dL	< 2  g/dL	

\* ULN used as reference if baseline was normal or missing; if baseline was abnormal (> ULN), baseline should be used as reference, for example, > ULN - 3 × ULN should be changed to > baseline - 3 × baseline if baseline was abnormal, according to CTCAE v5.

+ Haemoglobin values are taken from the Vaccine Trial Grading Scale 2007.

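### The Grade 3-4 laboratory summary has no row for neutrophils, although myelosuppression is a named albendazole risk and the restriction is not declared

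*SAP*

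**What the plan says.** Protocol 10.8 states, for laboratory tests, that the "percentage of subjects with on-treatment laboratory values of CTCAE 5.0 adapted scale grade 3 or 4 will be summarised". It names no subset of variables and leaves the details of the safety analyses to the SAP.

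SAP 10.3 sets out the haematology list: "Haematology variables to be summarized include: haematocrit, haemoglobin, red blood cells (RBC), white blood cells (WBC), neutrophils, lymphocytes, monocytes, eosinophils, basophils, platelets". The chemistry list is AST and ALT followed by "alkaline phosphatase (AP), glucose, creatinine, eGFR, blood urea nitrogen (BUN), total bilirubin, albumin, total protein, chloride, sodium, potassium and calcium". For graded values, however, it says that "a maximum of at least Grade 3 (CTCAE 5.0) for the laboratory parameters during treatment as defined in Appendix C will be summarized". The individual listing is given for subjects who rise to Grade 3 or higher on the same grading.

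The grading is in SAP Appendix C, Table C-1, titled "Definitions of Toxicity Grades 1, 2, 3, and 4 for Laboratory Values". Its rows are ALT, AST, ALP, bilirubin, haemoglobin (one row per sex), white blood cells, platelets, decreased glucose, creatinine, eGFR and albumin.

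Protocol 3.5.1.2 says: "Treatment with albendazole has been shown to occasionally cause myelosuppression". SAP 1.0 adds: "All analyses in this SAP are consistent with what is described in the study protocol unless otherwise noted in Section 13.0". Section 13.0 records several edits to Appendix C (eGFR in place of creatinine clearance, albumin units, liver grade definitions) but says nothing about which variables are graded.

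**The concern.** The protocol identifies a blood-count risk for albendazole, which three of the five Part 1 arms receive (7 days in Arms C and E, 3 days in Arm D). Protocol 3.5.2.1 pairs blood counts with liver tests as the monitored safety data. In the SAP, liver tests get toxicity grades, multiples of the upper limit of normal and eDISH plots. Neutrophils, the white cell type for which a severe fall is the usual worry with myelosuppression, get no severity count.

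At stake is whether the Part 1 safety report can state, by arm, how many subjects had a severe on-treatment fall in neutrophils, using measured values alone. Those tables will be read when regimens with and without albendazole are chosen for Part 2. A reader who takes SAP 1.0 at its word will also assume that the protocol's graded summary has been delivered in full.

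**Working it through.** The documents state no figure for this point, so there is none to reproduce. The check is a count, a comparison of reporting routes, and a small illustration.

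**1. Coverage of Table C-1**

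- Variables summarised (SAP 10.3): 10 haematology + 14 chemistry = 24.
- Table C-1: 12 rows, with haemoglobin on two of them, so 12 - 1 = 11 distinct variables.
- Coverage: 11/24 = 45.8%. By group it is 3 of 10 haematology variables (haemoglobin, WBC, platelets) and 8 of 14 chemistry variables.
- Not graded: 24 - 11 = 13. These are haematocrit, RBC, neutrophils, lymphocytes, monocytes, eosinophils, basophils, blood urea nitrogen, total protein, chloride, sodium, potassium and calcium.

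**2. Where a severe neutrophil value would appear**

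| Route | Source | What it shows | Limit |
|---|---|---|---|
| By-visit summary | SAP 10.3 | Minimum per arm and visit | No count of subjects |
| Shift tables | SAP 10.3 | Subjects going to low | No grade; baseline must be normal or high |
| WBC row | SAP Table C-1 | Graded count | Grade 3 only if total WBC is below 2.0 x 10^9/L |
| Adverse event tables | Protocol 9.3.4.2; SAP 10.2 | Graded event under its own term | Needs a judgement of clinical significance |
| Grade 3-4 laboratory count and listing | SAP 10.3 | Nothing for neutrophils | No row in Table C-1 |

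The baseline condition in the shift tables matters because protocol 6.2 sets no numerical neutrophil limit. A subject could enter with a low value, fall further, and not be counted. The graded table would handle this case: SAP 10.3 counts any post-baseline grade more extreme than the baseline grade.

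**3. Total WBC as a stand-in**

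Total WBC = neutrophils + all other white cells. Table C-1 grades WBC as 2 from below 3.0 down to 2.0, as 3 from below 2.0 down to 1.0, and as 4 below 1.0 (all x 10^9/L). Assume neutrophils of 0.5. The documents give no neutrophil cut-off, so both this value and calling it severe are assumptions.

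| Other white cells | Total WBC | WBC grade |
|---|---|---|
| 0.8 | 0.5 + 0.8 = 1.3 | 3 |
| 1.5 | 0.5 + 1.5 = 2.0 | 2 |
| 2.0 | 0.5 + 2.0 = 2.5 | 2 |
| 3.0 | 0.5 + 3.0 = 3.5 | at most 1 |

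With neutrophils at 0.5, WBC reaches Grade 3 only if the other cells are below 2.0 - 0.5 = 1.5. The WBC row therefore picks up a severe neutrophil fall only when the other white cells are low as well.

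**The case against.** The other side has a substantial case.

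- **Severe neutropenia would still be seen.** A reader might infer that it would go uncounted altogether. The documents do not support that. Neutrophils are in the by-visit and shift tables. Protocol 9.3.4.2 requires a new abnormality suggesting organ toxicity to be reported as an adverse event, and 9.3.4.6 requires it to be graded. SAP 10.2 tabulates events by maximum severity, and a severe related event also counts towards the toxicity rule in protocol 3.5.2.2. This stands, and it limits the point to the graded laboratory summary and its listing.
- **Eleven of 24 is not a proven shortfall of 13.** The adapted scale is in protocol Appendix 6, a separate attachment whose content is not shown. Some ungraded variables may have no grade to apply. This stands: the ratio describes coverage only.
- **The protocol leaves detail to the SAP.** Choosing variables in Appendix C can be read as supplying that detail. This stands in part: a subset is legitimate, but nothing says that one was chosen or why.
- **The vaccine trial scale in protocol 9.3.4.6 governs adverse event grading, not a laboratory table.** True, but Table C-1 already takes haemoglobin from that scale, so using it for other variables creates no difficulty.
- **The risk is modest.** Protocol 3.5.1.2 mentions liver enzymes first, calls myelosuppression occasional, and links regular counts to long courses; dosing here is at most 7 days. This stands and bears on priority.
- **Potassium.** Its absence might look equally serious because low potassium at screening is an exclusion. That same exclusion means baseline should be normal or high, so the shift tables would count a fall below normal. Potassium is a matter of completeness only.

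**Conclusion.** The point holds in a limited form. The Grade 3-4 laboratory counts and linked listing cover 11 of the 24 summarised variables and omit neutrophils. Protocol 10.8 names no such restriction, and SAP Section 13.0 does not declare one. As a result, the plan has no severity count for neutrophils that is independent of the investigator's decision to report an adverse event. The shift tables miss worsening from an already low baseline, and total WBC can stay below Grade 3 when neutrophils are very low.

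The conclusion does not depend on the neutrophil value assumed in the illustration, because the missing row is a matter of record. It does assume that the adapted scale grades neutrophils, which should be confirmed against Appendix 6. The documents do not show that a safety signal would be lost, or that all 13 ungraded variables should be graded. This is a minor safety-reporting gap with no effect on the primary analysis, the sample size or data collection.

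**What to change.** 1. Add neutrophils to SAP Table C-1, using the adapted scale in protocol Appendix 6.
2. Add the other collected variables that this scale grades, for example lymphocytes, potassium, sodium and calcium where it does so.
3. Add eosinophils, blood urea nitrogen and total protein on the vaccine trial scale named in protocol 9.3.4.6, footnoted in the way haemoglobin already is.
4. Produce the same Grade 3, Grade 4 and Grade 3-or-higher counts by arm, and the same subject listing, for the added rows.
5. Record in Section 13.0 any variable deliberately left ungraded, with a short reason.

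The cost is a longer Table C-1, more rows in one output and a longer listing. The variables are already collected (protocol Appendix 5) and already summarised under SAP 10.3, so no new measurement is needed.
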